8.2.4 FOLLOW-UP VISITS

Follow-up visits will be performed after Visit 8 for all subjects who had at least one dose of trial treatment. Follow-up visits will not be performed if:

- The subject is lost to follow-up
- The subject withdraws consent from the study
- The investigator and sponsor agree not to pursue further follow-up visits with the subject
- The subject dies

In these cases, the trial completion page of the eCRF must be filled out.

8.2.4.1 Visit 9

At Visit 9, the following procedures and assessments are performed:

- Pharmacokinetic and biomarker samples are taken
- Specified ophthalmological assessments: BCVA, SD-OCT, slit lamp, and IOP
- Vital signs and safety laboratory tests
- Review of concomitant medications
- AE reporting and evaluation

8.2.4.2 Visit 10

At Visit 10, the following procedures and assessments are performed:

- Specified ophthalmological assessments: BCVA, SD-OCT, slit lamp, and IOP
- Vital signs, physical examination, and safety laboratory tests
- Review of current medications
- AE reporting and evaluation

8.2.4.3 Safety Follow-up: Documented Phone Call

At Day 71 (28 days after end of treatment), the following assessments are performed by phone:

- Review of current medications
- AE reporting and evaluation

In addition, the Trial Completion page must be finalized and entered in the eCRF.

9 CLINICAL MONITORING

Clinical site monitoring is conducted to ensure that the rights and well-being of human subjects are protected, that the reported trial data are accurate, complete, and verifiable, and that the conduct of the trial is in compliance with the currently approved protocol/amendment(s), with GCP, and with applicable regulatory requirement(s).

- Monitoring for this study will be performed by the study CRO in accordance with the Clinical Monitoring Plan (CMP).
- A mix of on-site and centralized risk-based monitoring will be performed to ensure the safety of clinical subjects and the accuracy and completeness of study data.
- The sponsor will be provided with copies of monitoring reports per the timelines specified within the CMP.
- Details of clinical site monitoring tasks and scope are documented in the study’s CMP. The CMP describes in detail who will conduct monitoring, at what frequency monitoring will be done, at what level of detail monitoring will be performed, and the distribution of monitoring reports.
- Independent audits may be conducted by the sponsor in accordance with the Clinical Quality Oversight Plan to ensure monitoring practices are performed consistently across all participating sites and that monitors are following the CMP.

10 STATISTICAL CONSIDERATIONS

10.1 STATISTICAL DESIGN MODEL AND ANALYTICAL PLANS

The therapeutic effect of the treatment will be investigated in one single group of subjects, with no control group. The observed mean effect will be compared with 0 as reference value. Overall baseline and demographic data will be summarized using descriptive statistics.

Subject disposition (e.g., the number of subjects enrolled, completed, and discontinued) will be summarized and medical history data will be listed. Prior and concomitant medications taken from screening and during the study will be categorized by World Health Organization (WHO) classification for therapeutic class and drug name, listed and summarized by number and percentage of subjects.

Final analyses are not limited to the summaries described herein. Analytical details and assumptions will be fully presented in the SAP.

10.2 STATISTICAL HYPOTHESES

The null and alternative hypothesis for change from baseline in BCVA letter score as measured by ETDRS testing method are:

H_0 : Change from baseline in BCVA letter score = 0

H_1 : Change from baseline in BCVA letter score \neq 0 with $\alpha_1 = 0.20$

10.3 ANALYSIS DATASETS

Four analysis datasets are possible however, analyses may not necessarily be conducted with all four:

- **Intention-to-Treat (ITT) Dataset:** all enrolled subjects
- **Safety Dataset:** all subjects who received at least 1 dose of the study agent
- **Evaluable Dataset:** all subjects who complete at least 3 weeks of treatment during the 6-week treatment period
 - **Per Protocol Dataset:** a subset of the Evaluable Dataset comprised of subjects who have no major protocol violations

The presentation of baseline characteristics will be based on the ITT dataset. All safety analyses will be performed for the Safety Dataset. Analyses of the primary and exploratory endpoints will focus on the Evaluable and/or Per Protocol Datasets.

10.4 PLANNED ANALYSES

10.4.1 ANALYSIS OF THE PRIMARY ENDPOINT

The therapeutic effect of the treatment will be investigated in one single group of subjects, with no control group. The changes from baseline in BCVA will be compared with 0 as reference value. The study is not designed to detect significant changes in BCVA over time. However, using available data, including changes in BCVA from baseline, descriptive summarization will be developed. Of particular interest will be the within-subject changes in BCVA from baseline and their distribution around a null value of zero.

10.4.2 ANALYSIS OF THE SECONDARY ENPOINT

Safety will be assessed for the following endpoints:

- Incidence, seriousness, and severity of adverse events
- Changes from baseline in clinical laboratory values
- Changes from baseline in physical examination
- Changes from baseline in vital signs

All treated subjects (i.e., all subjects who received at least 1 dose of the study agent) will be included in the safety evaluation. Safety analyses will be descriptive in nature and will be based on accepted standards.

Tabulations of frequencies/proportions will be used for the evaluation of categorical (qualitative) data, and tabulations of descriptive statistics will be used to analyze continuous (quantitative) data.

10.4.3 EXPLORATORY ANALYSES

Observed values as well as changes from baseline in CST, IRF, SRF, and PED as measured by SD-OCT and fundus photography/FA will be summarized using descriptive statistics. Pharmacokinetic, biomarker, and pharmacogenomic analyses will be carried out using an exploratory approach to investigate the potential influence on the therapeutic response of ALK4290.

10.4.4 PLANNED INTERIM ANALYSES

Continuous data monitoring will be performed. One interim analysis will be performed when 2/3 of all entered subjects have reached Day 15 (Visit 4). It will include only the primary and a subset of the secondary endpoints, (i.e., mean change in BCVA as measured by ETDRS and the accumulated AE information). Recruitment into the trial will be stopped if the interim analysis shows relevant safety problems with ALK4290. No formal futility analysis will be conducted.

10.5 SAMPLE SIZE

A total of 30 subjects will be enrolled in the study with the intent of obtaining ~25 evaluable subjects who have completed at least 3 weeks of treatment and evaluations through Visit 4. Subjects who discontinue prior to Visit 4 may be replaced. Subjects who withdraw or are withdrawn during screening will be replaced. The study is not powered for detecting statistically significant differences in therapeutic parameters in subjects with wAMD receiving ALK4290. However, the proposed sample size may be sufficient to identify trends in the effects of ALK4290 and in the relationship between dose and response.

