8.2.3 END OF TREATMENT

All end of treatment (EOT) study-related procedures will be conducted at the conclusion of 6 weeks of treatment on Day 43 \pm 1. However, for subjects who withdraw consent from the study, no study procedures will be done thereafter. For subjects that withdraw from the study agent, EOT procedures and follow up visits are to occur as per the protocol. Excluding cases of medical emergency, but prior to the discontinuation of a subject from the clinical study for disease worsening, the study investigator should discuss each case of discontinuation with the sponsor.

8.2.3.1 Visit 8

At Visit 8, the following procedures and assessments are performed:

- Pharmacokinetic and biomarker samples are taken
- All ophthalmological assessments: BCVA, SD-OCT, fundus photography/FA, slit lamp, and IOP
- Vital signs, physical examination, safety laboratory tests, **Poland only:** serum pregnancy test (in women of childbearing potential), and 12-lead ECG
- Review of concomitant medications
- AE reporting and evaluation

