7. End of Treatment (EOT) visit (Visit 8): all study related procedures will be conducted at the conclusion of 6 weeks of treatment on Day 43 ±1. Withdrawal of consent is allowed at any time. For subjects who withdraw consent from the study, no study procedures will be done thereafter. For those that withdraw from the study agent, follow-up visits are to occur as per the protocol. Excluding cases of medical emergency, but prior to the discontinuation of a subject from the clinical study for disease worsening, the study investigator should discuss each case of discontinuation with the sponsor.
8. Adverse events and concomitant medications will be assessed at every study visit as well as recorded at any unscheduled subject contact (e.g., unscheduled phone calls, etc.). Following completion of study agent treatment (Visits 2-8), all current medications will be assessed in the follow-up period.
9. Pregnancy test required in Poland only per Inclusion Criteria.

5. Study Treatments

This is a single arm, open-label study. All subjects will receive the investigational treatment ALK4290 at a daily dosage of 800 mg administered orally twice a day as 400 mg tablets for 6 weeks.

6. Sample Size and Power Considerations

A total of 30 subjects will be enrolled in the study with the intent of obtaining approximately 25 evaluable subjects who would complete at least 3 weeks of treatment and evaluations through Visit 5 (Day 22). Subjects who discontinue prior to Day 22 may be replaced. Subjects who withdraw or are withdrawn during screening (prior to completing V2) will be replaced. The study is not powered for detecting statistically significant differences in therapeutic parameters in subjects with wAMD receiving ALK4290.

7. Data Preparation

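### Protocol 10.5 ties its 3-week evaluable criterion and its replacement cut-off to Visit 4 (Day 15, two weeks), while SAP 6 uses Visit 5 (Day 22)

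*Protocol*

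**What the plan says.** Protocol 10.5 sets enrolment ("A total of 30 subjects will be enrolled in the study") "with the intent of obtaining ~25 evaluable subjects". It describes those evaluable subjects as having "completed at least 3 weeks of treatment and evaluations through Visit 4". On replacement it says: "Subjects who discontinue prior to Visit 4 may be replaced".

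The Evaluable Dataset in Protocol 10.3 is "all subjects who complete at least 3 weeks of treatment during the 6-week treatment period". It names no visit. SAP 8.3 gives the same definition, and SAP 14 runs the primary BCVA analysis on that set.

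SAP 6 restates the size target for subjects who "would complete at least 3 weeks of treatment and evaluations through Visit 5 (Day 22") and allows replacement of subjects who discontinue before Day 22. SAP 21, the section for changes from the protocol-stated analyses, is marked not applicable.

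The schedule tables in both documents put Visit 4 at Day 15 and Visit 5 at Day 22, each with a window of one day either side.

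**The concern.** Protocol 10.5 names a treatment duration and a visit in one phrase, and they are a week apart. The replacement rule then uses the earlier of the two, while membership of the primary analysis set uses the later.

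This leaves Days 15 to 21 as a gap. A subject who stops treatment in those days has had less than three weeks of study agent, so is not in the Evaluable set. That subject has also passed the only point before which the Protocol offers replacement. SAP 9.1 imputes no missing outcome data, so each such exit lowers the number available to the primary analysis.

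Exits in that week are foreseeable. BCVA is measured at Visit 4, and Protocol 5.3.2 lists a loss of five letters or more among its criteria for considering withdrawal.

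The two documents also give sites and the sponsor different cut-offs for the same decision, and neither acknowledges the difference.

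**Working it through.** **1. Convert visits to weeks of treatment.** Dosing starts on Day 1, so elapsed weeks = (Day − 1)/7. Check this against the plan's own anchor: Protocol 8.2.3 places end of treatment at the "conclusion of 6 weeks of treatment on Day 43", and (43 − 1)/7 = 6.0, so the convention holds.

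- Visit 4: Protocol 10.4.4 gives the day ("2/3 of all entered subjects have reached Day 15 (Visit 4"). (15 − 1)/7 = 2.0 weeks. With the one-day window it runs from (14 − 1)/7 = 1.86 to (16 − 1)/7 = 2.14 weeks, so the window cannot bridge the gap.
- Visit 5: (22 − 1)/7 = 3.0 weeks.

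The three-week visit is therefore Visit 5, one visit later than Protocol 10.5 names.

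**2. Reproduce the plan's size.** No effect size, SD, power or dropout rate is given, so there is no formula to reproduce. The implied non-evaluable share is 1 − 25/30 = 16.7%. Inflating 25 by that share returns 25/(1 − 1/6) = 30, which is circular.

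**3. Set the rules side by side.**

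| Subject stops treatment | Evaluable (Protocol 10.3, SAP 8.3) | Within Protocol 10.5 replacement rule | Within SAP 6 replacement rule |
|---|---|---|---|
| Before Visit 4 (Day 15) | No | Yes | Yes |
| Days 15–21 | No | No | Yes |
| Day 22 or later | Yes | Not needed | Not needed |

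The documents disagree in the middle row only.

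**4. Count the loss.** Suppose every exit before Visit 4 is replaced, so that 30 subjects reach Visit 4, and k of them stop on Days 15–21 without replacement. Then evaluable = 30 − k: k = 5 leaves 25, and k = 6 leaves 24.

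**5. Put a range on it.** Let p be the chance that a subject who reaches Visit 4 stops before Day 22. The documents give no value, so p is an assumption. The evaluable count is then Binomial(30, 1 − p).

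| Assumed p | Expected evaluable, 30(1 − p) | P(at least 25) |
|---|---|---|
| 2% | 29.4 | about 1.00 |
| 5% | 28.5 | 0.997 |
| 10% | 27.0 | 0.93 |
| 15% | 25.5 | 0.71 |
| 20% | 24.0 | 0.43 |

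**6. A second view.** The gap covers 7 of the 21 days in which an exit makes a subject non-evaluable. If early exits were spread evenly over those days (also an assumption), one third would fall in the gap. Five early exits would leave 30 − 1.7 = 28.3 evaluable, and ten would leave 30 − 3.3 = 26.7. Both exceed 25.

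**The case against.** The strongest defence is that nothing here breaks the trial. The two conditions in Protocol 10.5 are compatible: three weeks is the stricter, and the Visit 4 condition is merely redundant. The target is approximate, replacement is optional, and both documents say the study is not powered, so no error rate or power claim depends on reaching 25. All of that stands, and it limits the size of the point. It does not remove the mismatch between the replacement cut-off and the Evaluable definition, or between the two documents.

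A reader might infer more than the text supports:

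- *That a Day 15–21 exit counts toward the 25.* It does not. The conditions are joined by a conjunction, so such a subject fails the three-week condition and counts only toward the 30 enrolled.
- *That such a subject cannot be replaced.* The Protocol does not say so. It gives a permissive rule with a cut-off and is silent after it, and SAP 6 expressly allows replacement before Day 22.
- *That the primary analysis will fall short of 25.* The margin of five has to be used up first. In addition, the Evaluable count at Day 22 is not the n of the primary t-test, which needs BCVA at Visit 8.

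It can also be argued that the SAP already settles the matter. SAP 1 says the SAP supersedes the protocol on statistical analysis methods. Whether to replace a subject is a decision made during conduct, so that clause does not clearly reach it. SAP 1 also cites Clarification Memorandum #1 (12JUL2018), which is not among the documents and may address the point.

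**Conclusion.** The inconsistency is certain on the page. Protocol 10.5 pairs three weeks of treatment with a two-week visit and stops its replacement offer there. This conflicts with the Evaluable definition in both documents and with SAP 6 on both milestone and cut-off, and SAP 21 does not record the difference.

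The consequence is modest. It is confined to exits on Days 15–21, and up to five of them still leave 25 evaluable if there are no other unreplaced losses. The shortfall becomes likely only if the exit rate in that single week is high: at an assumed 20%, the chance of reaching 25 is 0.43. These probabilities rest on an assumed rate, independent exits and full replacement of everyone who leaves before Visit 4. If some of those are not replaced, which the Protocol permits, part of the margin is already spent. The conclusion is also subject to what the unseen memorandum says.

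**What to change.** In Protocol 10.5, change both mentions of Visit 4 to Visit 5 (Day 22), so that the milestone and the replacement cut-off match the Evaluable definition and SAP 6. In SAP 21, replace the not-applicable entry with a note of the difference from Protocol Version 3.0. If Clarification Memorandum #1 already makes the change, cite it there.

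The cost is a one-line protocol correction, with the IRB/IEC submission that Protocol 12.2 requires for any modification, and possibly a few extra replacement subjects. The enrolment target of 30 and the evaluable target of about 25 need not change.

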11 SOURCE DOCUMENTS AND ACCESS TO SOURCE DATA/DOCUMENTS

Each participating site will maintain appropriate medical and research records for this trial, in compliance with ICH E6 R2 and regulatory and institutional requirements for the protection of confidentiality of participants. Each site will permit authorized representatives of regulatory agencies, the IRB/IEC, the sponsor, or the sponsor's representatives to examine (and when permitted by applicable law, to copy) clinical records for the purposes of quality assurance reviews, audits, and evaluation of the study safety, progress, and data validity.

Source data are all information, original records of clinical findings, observations, or other activities in a clinical trial necessary for the reconstruction and evaluation of the trial. Examples of these original documents and data records include, but are not limited to, hospital records, clinical and office charts, laboratory notes, memoranda, participant's memory aids or evaluation checklists, pharmacy dispensing records, recorded audio tapes of counseling sessions, recorded data from automated instruments, copies or transcriptions certified after verification as being accurate and complete, microfiches, photographic negatives, microfilm or magnetic media, x-rays, and participant files and records kept at the pharmacy, at the laboratories, and medico-technical departments involved in the clinical trial.

It is not acceptable for the eCRF to be the only record of a subject's participation in the study. This is to ensure that anyone who would access the medical record has adequate knowledge that the subject is participating in a clinical trial. Source document templates will be developed for this study.

12 ETHICS/PROTECTION OF HUMAN SUBJECTS

12.1 ETHICAL STANDARD

The study will be conducted in compliance with the protocol, the principles laid down in the Declaration of Helsinki, and in accordance with the ICH Harmonized Tripartite Guideline for GCP.

12.2 INSTITUTIONAL REVIEW BOARD

This protocol and any accompanying material to be provided to the subject (such as advertisements, subject information sheets, or descriptions of the study used to obtain informed consent) will be submitted by the investigator to an IRB or IEC. Approval from the IRB/IEC must be obtained before starting the study and should be documented in a letter to the investigator specifying the protocol number, protocol version, documents reviewed, and date on which the committee met and granted the approval.

All changes to the consent form will be IRB approved; a determination will be made regarding whether previously consented participants need to be re-consented.

Any modifications or amendment to the protocol must also be submitted to the IRB/IEC for approval prior to implementation.

12.3 INFORMED CONSENT PROCESS

12.3.1 CONSENT FORMS

Consent forms describing in detail the study agent, study procedures, and risks are given to the participant and written documentation of informed consent is required prior to any invasive study procedures.

12.3.2 CONSENT PROCEDURES AND DOCUMENTATION

It is the responsibility of the investigator or designee to obtain written informed consent from each subject participating in this study and/or their legally authorized representative after adequate explanation of the aims, methods, objectives, and potential hazards of the study and prior to undertaking any study-related procedures.

Subjects should have the opportunity to discuss the study with their family members or other advisors and the time to consider participation in the trial carefully. The participants may withdraw consent at any time throughout the course of the trial. The rights and welfare of the participants will be protected by emphasizing to them that the quality of their medical care will not be adversely affected if they decline to participate in this study.

The investigator or designee must utilize an IRB/IEC-approved consent form that contains the elements required by ICH GCP and applicable regulatory requirements for documenting written informed consent. Each informed consent will be appropriately signed and dated by the subject and/or their legally authorized representative and the person obtaining consent. A copy of the signed consent form will be provided to the subject and/or their legally authorized representative. By signing the informed consent form, all parties agree they will complete the evaluations required by the study, unless they withdraw voluntarily or are terminated from the study for any reason.

Investigators will be expected to maintain a screening log of all potential study candidates that includes limited information about the potential candidate (e.g., date of screening).

All subjects who provide consent will be assigned a unique study number. This number will be used to identify the subject throughout the clinical study and must be used on all study documentation related to the study subject. Once a number is assigned to a subject, that number will remain with that study subject and will not be reused.

If an individual's medical chart or results of diagnostic tests performed as part of an individual's regular medical care are going to be used for screening, written informed consent must be obtained prior to review of that information.

12.4 DATA CONFIDENTIALITY

Subject confidentiality is held in strict trust by the participating investigators, their staff, the sponsor and their agents. This confidentiality is extended to cover testing of biological samples and genetic tests in addition to the clinical information relating to participants. Therefore, the study protocol, documentation, data, and all other information generated will be held in strict confidence. No information concerning the study or the data will be released to any unauthorized third party without prior written approval of the sponsor.

The study monitor, other authorized representatives of the sponsor, representatives of the IRB/IEC or government regulatory agencies may inspect documents and records required to be maintained by the investigator, including but not limited to, medical records (office, clinic, or hospital) and pharmacy records for the participants in this study. The clinical study site will permit the study monitor access to such records.

The investigator must assure that subjects' anonymity will be strictly maintained and that their identities are protected from unauthorized parties. Only subject initials and an identification code (i.e., not names) should be recorded on non-local lab samples, requisitions and any documents submitted to the CRO, sponsor and/or IRB/IEC. The investigator must keep a subject log showing codes, names, and addresses for all subjects screened and for all subjects enrolled in the trial. The study participant's contact information will be securely stored at each clinical site for internal use during the study. At the end of the study, all records will continue to be kept in a secure location for as long a period as dictated by local IRB/IEC and Institutional regulations.

